## 14.4 Feasibility:

All sites of the participating study groups may include patients in this study. The expected rates for inclusion per year were estimated by the numbers of patients that were submitted to the former European WM study. In addition, prior to site selection a feasibility has to be performed. The number of study sites will be around 30. The following inclusion rates will be attainable in the study:

Involved study groups	Patients accrual
GLA ([name]/Germany)	15 / year
Greek Myeloma Study Group ([name], Greece)	20 / year
Austria ([name])	5 / year

## 14.5 Analysis populations

## 14.5.1 Core Analysis Population

The core analysis population consists of all patients randomized in the study evaluated in the group they were randomized to. Patients with missing or unevaluable response assessment12 months after randomization (primary endpoint) will be excluded from analysis of the primary outcome. Patients who progressed or died within 12 months from randomization are not in CR/VGPR at this time point and are thus classified as non-responders (i.e. CR/VGPR="no"). We do not impute missing or unevaluable response assessment because we expect those missing values as missing at random since regular follow-up for lymphoma progression is foreseen also in case of early treatment discontinuation. We will make sure by communication and monitoring that the follow-up schedule will be maintained in case of early treatment discontinuation irrespective of the treatment group. As a sensitivity analysis for the primary outcome, we will perform a conservative imputation of the CR/VGPR rate at 12 months from randomization by defining patients alive without progression and with missing or unevaluable response assessment at this time point as non-responders (i.e. CR/VGPR="no"). The group comparisons of secondary efficacy outcomes represent further sensitivity analyses with different approaches to missing or unevaluable response assessment at 12 months from randomization (e.g. last observation carried forward in best response, counting treatment discontinuation as event in TTF, and censoring at last staging in PFS).

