## 12.3 Follow up phase

As soon as the treatment is stopped because of non-tolerated toxicity, patients will enter followup and will be clinically evaluated every 3 months after the last treatment for 2 years and then every 6 months for 3 additional years or until progression of disease (until end of study).

Patients with progression or starting of new anti-lymphoma therapy will be followed up only for survival data and data with regard to further treatment of WM every 6 months until end of study.

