## 14.2 Sample size estimation

## RCT - arms A and B:

The sample size calculation is based on the comparison of the primary endpoint (CR / VGPR rate) between the arms A and B using the one-sided chi-square test. According to Treon et al. (NEJM 2015) the CR / VGPR rate in WM patients treated with Ibrutinib is about 16%. We see an increase from 16% to 35% CR / VGPR as a clinically relevant increase, which corresponds to a more than doubling of deep remissions. Deep remissions correlate with PFS and the disease-free interval, thus we assume that the risk-benefit ratio justifies the addition of Carfilzomib when we achieve this improvement. Assuming a CR / VGPR rate of 35% in patients treated with Carfilzomib and Ibrutinib, this scenario requires a number of 94 patients (i.e. 47 patients per group) to reach a power of 80% at a one-sided type one error of 0.10. It is expected that the rate of withdrawal in the study is smaller than 5%. In addition to the drop-out rate of 5%, patients who were randomized but withdrew consent before the start of therapy may be replaced until the end of the recruitment period. According to this, the study will enroll approximately 99 patients in the arms A and B in total.

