## 14.3 Statistical analysis

The primary study endpoint CR / VGPR rate will be evaluated following the intention to treat principle. The chi square test will be used for the analysis of the primary endpoint to test the CR / VGPR rate in the arms A and B at the 10% significance level (one-sided) in the core analysis population. The corresponding set of null and alternative hypothesis is:

H0: RRA  $\leq$  RRB

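### The primary analysis leaves out patients alive without progression who lack a 12-month response, against the stated intention-to-treat principle, and its missing-at-random reason fails for those who start new therapy before month 12

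*Protocol*

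**What the plan says.** Section 14.3 states the principle: "The primary study endpoint CR / VGPR rate will be evaluated following the intention to treat principle". It runs the chi-square test in the core analysis population and draws the conclusion from that test (one-sided p of at most 0.10, with arm A's rate above arm B's). Section 12.7.1 appeals to intention to treat as well, as the reason for keeping patients later found ineligible.

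Section 14.5.1 defines the core population as all randomised patients in their randomised arm, and then adds: "Patients with missing or unevaluable response assessment12 months after randomization (primary endpoint) will be excluded from analysis of the primary outcome". Three further statements in that section matter:

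- Patients who progress or die within 12 months count as CR/VGPR 'no'.
- Missing responses are not imputed, because they are expected to be missing at random; the reason given is that "regular follow-up for lymphoma progression is foreseen also in case of early treatment discontinuation".
- A sensitivity analysis counts patients alive without progression and without a usable assessment as non-responders.

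On follow-up, section 12.3 says: "Patients with progression or starting of new anti-lymphoma therapy will be followed up only for survival data" (the sentence goes on to add data on further WM treatment). The survival follow-up paragraph in section 5 says explicitly that this also applies to patients who receive new therapy without having progressed.

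**The concern.** The test that decides the trial is a complete-case test, although the plan calls it intention to treat and defines its population as all randomised patients.

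The reason given for accepting this does not hold for one identifiable group. A patient who starts new anti-lymphoma therapy before month 12 without progression moves to survival follow-up, so no 12-month response is scheduled. The non-responder rule names only progression and death, so that patient leaves the denominator. Section 14.1.2 counts the same event as a failure in time to treatment failure. The primary analysis therefore discards an outcome that the protocol elsewhere calls a failure.

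A smaller route is possible. Appendix 21.1 takes baseline IgM at day 1 of cycle 1, so a randomised patient who is never treated may have no baseline against which response can be judged.

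At stake is a decision at a one-sided 10% level with about 50 patients per arm, where a few exclusions matter.

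**Working it through.** **Inputs from section 14.2.** Control rate: "the CR / VGPR rate in WM patients treated with Ibrutinib is about 16" (per cent). Experimental rate: "Assuming a CR / VGPR rate of 35% in patients treated with Carfilzomib and Ibrutinib". Error rates: "to reach a power of 80% at a one-sided type one error of 0.10". Expected withdrawal is below 5%, with no figure by arm. I split the 99 patients 50 to arm A and 49 to arm B. All missing rates by arm are my assumptions.

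**The plan's own figure.** With the pooled rate (0.16 + 0.35)/2 = 0.255:

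n per arm = [1.2816·√(2·0.255·0.745) + 0.8416·√(0.16·0.84 + 0.35·0.65)]² / 0.19² = 46.5, so 47 per arm and 94 in total. Then 94/0.95 = 98.9, so 99. The sample size is right, and it allows for 5% loss.

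**Type I error of the complete-case test.** Let the true CR/VGPR rate over all randomised patients be 16% in both arms, and let every missing patient be a non-responder. With missing fractions mA and mB, the rates among analysed patients are 0.16/(1 − mA) and 0.16/(1 − mB). The rejection probability (uncorrected z of at least 1.2816) is enumerated exactly from two binomials on 50 − i and 49 − j patients, then averaged over i ~ Bin(50, mA) and j ~ Bin(49, mB).

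| Missing A / B | Analysed rate A / B | Type I error |
|---|---|---|
| 0% / 0% | 16.0% / 16.0% | 0.108 |
| 5% / 5% | 16.8% / 16.8% | 0.103 |
| 5% / 0% | 16.8% / 16.0% | 0.124 |
| 10% / 5% | 17.8% / 16.8% | 0.126 |
| 20% / 5% | 20.0% / 16.8% | 0.188 |

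The right comparator is 0.108, the test's own exact size at 50 versus 49, rather than 0.10.

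**How few patients decide the result.** Take 8/49 responders in arm B and 13 in arm A.

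- All 50 counted: 13/50 = 26.0%, pooled rate 21/99 = 0.2121, standard error 0.0822, z = 0.0967/0.0822 = 1.177, p = 0.120. No success.
- Two non-responders excluded: 13/48 = 27.1%, pooled rate 21/97 = 0.2165, standard error 0.0836, z = 0.1076/0.0836 = 1.286, p = 0.099. Success.

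**Power if missing counts as non-response.** Exact power at 50 versus 49, with the design rates multiplied by (1 − missing). This assumes that missing patients would have responded as often as the others.

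| Missing A / B | Rates A / B | Power |
|---|---|---|
| 5% / 5% | 33.3% / 15.2% | 80.6% |
| 10% / 10% | 31.5% / 14.4% | 78.6% |
| 10% / 2% | 31.5% / 15.7% | 73% |
| 20% / 2% | 28.0% / 15.7% | 59% |

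For comparison, 47 per arm with complete data has exact power 81.2%. If the missing patients really are non-responders and 35% and 16% are rates over all randomised patients, counting them as 'no' costs nothing: power is 82.4% at 50 versus 49.

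**The case against.** Most early stopping does not lead to a missing response, and section 14.5.1 states its rule, its reason and a mitigation openly.

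- Under sections 11.1 and 11.3.2.1, an arm A patient who stops one drug for toxicity may continue the other and is still on protocol treatment.
- Patients who stop treatment altogether for toxicity are seen every 3 months with quantitative immunoglobulins (section 12.3 and Table 3), and response rests mainly on IgM.
- Section 14.5.1 undertakes to keep up follow-up in both arms.
- The non-responder analysis is prespecified, so a result that depended on missing data would be visible.
- Counting missing as failure is a choice of estimand. It is conservative for each rate but not unbiased.

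All of this stands, and it rules out several stronger readings that a reader might infer:

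- That every patient without an evaluable 12-month response is dropped. Early progressions and deaths are kept as non-responders.
- That carfilzomib toxicity will inflate arm A's rate. The protocol gives no missing rate by arm. Equal loss of non-responders produces no inflation, and the bias can run the other way if the missing patients would have responded.
- That patients who withdraw are removed because "patients who were randomized but withdrew consent before the start of therapy may be replaced until the end of the recruitment period". That sentence concerns recruitment numbers; section 14.5.1 still includes everyone randomised in the core population.
- That the error rate is badly out of control. With 10%, 20% or 30% missing in arm A against 2% in arm B, all non-responders, it would be 0.14, 0.19 or 0.29. Nothing in the protocol supports such rates; it expects under 5% withdrawal.

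The objection does not remove the conflict in wording or the gap for patients who start new therapy. The sensitivity analysis does not cure them either: if the two analyses disagree, section 14.3 still declares success on complete cases.

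**Conclusion.** The point holds as a conflict within the protocol and a gap in its missing-data reasoning. The deciding test excludes patients alive without progression who lack a usable 12-month response, contrary to sections 14.3 and 12.7.1 and to the population definition in 14.5.1 itself. For patients who start new therapy before month 12 without progression, the missing-at-random reason is contradicted by the protocol's own follow-up rules.

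The likely size is modest. At 5% loss in each arm there is no inflation; at 5% in arm A only, the type I error goes from 0.108 to 0.124. It becomes material only with clearly unequal loss (0.188 at 20% and 5%). These figures assume that all missing patients are non-responders and that the true rate is 16% in both arms. The protocol gives no frequency for new therapy without progression before month 12, so the number affected is unknown.

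This is an exploratory phase II trial with the alternative analysis already prespecified. The change is recommended; the flaw does not invalidate the design, and the sample size is correct.

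**What to change.** In sections 14.3 and 14.5.1, and in the synopsis:

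- Make the planned non-responder analysis of all randomised patients the primary analysis.
- Add new anti-lymphoma therapy before the 12-month assessment to the events classified as CR/VGPR 'no', beside progression and death.
- Keep the complete-case analysis as the sensitivity analysis.

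Both analyses are already planned, so the change is one of wording and order, with no new data collection. The costs are slightly lower reported response rates and some power: small if loss is about 5% per arm, but falling below 75% if loss is concentrated in arm A, as the second table shows. In that unequal case the complete-case result is also least trustworthy, so the lost power is not a reason to keep the present rule.

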## 14.5.2 Safety population

The safety population includes patients who started the respective treatment (Ibrutinib without or with Carfilzomib) and groups patients according to the treatment given, irrespective of the randomization result.

## 15. INDEPENDENT DATA SAFETY MONITORING COMMITTEE

An independent DSMC will review ongoing safety data throughout the study. The DSMC includes at least three independent members (2 experts in WM and one independent statistician). Review of the safety data by the DSMC will take place based on the safety analyses, which will be performed for all patients after the first 6 patients in arm A have completed the first 6 cycles of treatment with ongoing recruitment. Additionally, a second DSMC will take place after 30 patients in arm A completed 6 cycles or at the latest after 18 months of

treatment whichever comes earlier. All data presented at the meeting will be considered confidential. Following each meeting the DSMC will prepare a report and may recommend changes in the conduct of the study. Details on the work of the DSMC will be described in a specific DSMC charter, to be jointly agreed upon the DSMC members and the sponsor.

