## Data and Safety Monitoring Committee (DSMC)

A DSMC will be installed and composed of 3 members, including a statistician, who are not involved in the execution of the study. The data of all patients will

	be reviewed by the independent DSMC at the time point when the 6 th patient has completed 6 cycles of treatment in arm A. The second analyses will be reviewed when the 30 th patient in arm A completed 6 cycles or at the latest after 18 months of treatment, whichever comes earlier. The DSMC will give a benefit / risk assessment for the study and recommendations for continuation / discontinuation of the study according the safety data of the patients. (for more information see section 15 of the protocol).
Planned number of patients:	approximately 99 patients
Number of study centers	approximately 30 sites in the European Union
Investigational product	Carfilzomib, Ibrutinib
Statistical Methods	The primary goal of this study is to explore the efficacy of Carfilzomib in combination with Ibrutinib compared to Ibrutinib alone in the treatment of WM. Sample size estimation: RCT - Arms A and B:
	The sample size calculation is based on the comparison of the primary endpoint (CR / VGPR rate at 12 months from randomization) between the arms A and B using the one-sided chi-square test. According to Treon et al. (NEJM 2015) the CR / VGPR rate in WM patients treated with Ibrutinib is about 16%. Assuming a CR / VGPR rate of 35% in patients treated with Carfilzomib / Ibrutinib, this scenario requires a number of 94 patients in total (i.e. 47 patients per group) to reach a power of 80% at a one-sided type one error of 0.10. It is expected that the rate of withdrawal in the study is smaller than 5%. In addition to the drop-out rate of 5%, patients who were randomized but withdrew consent before the start of therapy may be replaced until the end of the recruitment period. According to this, the study will enroll approximately 99 patients in the arms A and B in total. Statistical analysis of primary and secondary endpoints in the RCT: The primary study endpoint CR / VGPR rate will be evaluated following the intention to treat principle. The chi square test will be used for the analysis of the primary endpoint to test the CR / VGPR rate in the arms A and B at the 10% significance level (one-sided) in the core analysis population. The corresponding set of null and alternative hypothesis is: H0: RRA ≤ RRB HA: RRA > RRB

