## **11.3.2 Dose modifications for Carfilzomib**

# 11.3.2.1 Dosage adjustments, delays, rules for withholding or restarting, permanent discontinuation

Carfilzomib will be discontinued, temporarily delayed, or dosage temporarily reduced, in the event of a treatment-related adverse event that, in the opinion of the investigator, warrants the discontinuation, temporary delay or dose reduction, as indicated in Table 5 and Table 6. The patient will be considered on protocol treatment while receiving either Carfilzomib and / or lbrutinib (i.e. if either Carfilzomib or lbrutinib are discontinued or interrupted, the patient is still considered on treatment if still taking the other investigational product). If day 1 of a cycle is delayed, day 1 of subsequent cycles should be adjusted accordingly to maintain the 28-day cycle duration. However, if a within-cycle dose is delayed, then the dates of the subsequent within-cycle doses should not be adjusted. If Carfilzomib administration does not commence

within the allowable window of the scheduled administration date, then this dose will be considered a missed dose with continuation of the subsequent cycles. Administration may resume at the next planned dosing date. A missed dose will not be made up. Carfilzomib must be discontinued permanently if a delay of more than 6 weeks is required due to unresolved toxicity.

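### Both patient-count DSMC reviews wait for arm A patients to complete 6 cycles, the first has no calendar limit, and none is scheduled after the second although most carfilzomib is given later

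*Protocol*

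**What the plan says.** Section 15 of the protocol opens with a general mandate: "An independent DSMC will review ongoing safety data throughout the study". It then names two reviews.

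- **First review.** In section 15 it takes place "after the first 6 patients in arm A have completed the first 6 cycles of treatment with ongoing recruitment". In the synopsis (Data and Safety Monitoring Committee) it takes place when the 6th "patient has completed 6 cycles of treatment in arm A". Neither text gives a latest date.
- **Second review.** Section 15: "a second DSMC will take place after 30 patients in arm A completed 6 cycles or at the latest after 18 months" of treatment. The synopsis agrees: "or at the latest after 18 months of treatment, whichever comes earlier". Neither text says when the 18 months begin.

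Both places say that the reviews cover all patients. Neither schedules a later review. Section 15 adds: "Details on the work of the DSMC will be described in a specific DSMC charter".

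Section 11.3.2.1 bears on who counts as having completed cycles of treatment. If one drug is stopped, "the patient is still considered on treatment if still taking the other investigational product".

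**The concern.** A safety review triggered only by completers has a timing rule that works against its purpose: the more patients stop early for toxicity, the longer the committee waits. The second review has a time limit, but the first has none of its own.

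The two scheduled reviews also sit early in the trial. Carfilzomib runs for 24 cycles (section 11.1) and recruitment runs from 18.02.2021 to Q2 2024 (section 9.1), so the last patients receive carfilzomib until about spring 2026. Section 13.1 notes that the two drugs are not approved in this combination for this indication. Section 7.7 names the DSMC as one of the measures that support a favourable benefit-risk balance, and section 12.7.3 makes it the source of recommendations to stop or change the study. If the protocol is followed exactly as written, the committee is scheduled to see only an early part of the exposure.

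**Working it through.** **Inputs from the protocol.** Carfilzomib schedule (sections 7.6.3 and 11.1); about 99 patients allocated 1:1, with 47 per arm required (sections 9.1, 12.5, 14.2), so 47 to 50 in arm A; first patient in 18.02.2021 and last in Q2 2024, about 38-40 months (section 9.1); feasibility accrual of 15 + 20 + 5 = 40 per year (section 14.4), so 99/40 = 2.475 years = 29.7 months.

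**Assumptions, not in the protocol.** Even accrual; early-stopping rates of 30% and 50%; carfilzomib discontinuation of 0-5% per month.

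**Step 1: reproduce the planned dose.** Cycle 1: 20 + 70 + 70 = 160 mg/m². Cycles 2-12: 11 × 210 = 2310. Cycles 13-24: 12 × 140 = 1680. The total is 4150 mg/m², which matches section 7.6.3. Cycles 1-6 give 160 + 5 × 210 = 1210 mg/m², or 29%. The other 71% comes after the point that either patient-count trigger requires.

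**Step 2: timing of the first review (synopsis reading, the 6th completer).** Arm A accrual is 50/40 = 1.25 per month on the stated dates, or 40/2/12 = 1.67 per month at the feasibility rate. Six cycles are 168 days = 5.5 months. If a fraction q fails to complete, about 6/(1 − q) patients must enter, and the review falls at about (6/(1 − q) − 1)/rate + 5.5 months.

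| q | Entrants needed | Month at 1.67 per month | Month at 1.25 per month | Delay (months) |
|---|---|---|---|---|
| 0 | 6.0 | 8.5 | 9.5 | – |
| 30% | 8.6 | 10.1 | 11.6 | 2.57/1.67 = 1.5 to 2.57/1.25 = 2.1 |
| 50% | 12.0 | 12.1 | 14.3 | 6/1.67 = 3.6 to 6/1.25 = 4.8 |

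**Step 3: share of arm A carfilzomib given after the second review.** Each patient enters at evenly spaced times and follows the dose calendar. The share is the sum of doses due after the review divided by the sum of all doses.

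| Recruitment | After month 18 from first patient in, no attrition | Same, 1-5% per month stopping | Month of 30th completer | After the 30th completer, no attrition |
|---|---|---|---|---|
| 40 months | 78% | 74-77% | 28.7-30.2 | about 48-52% |
| 38 months | 77% | 72-76% | 27.6-29.0 | about 48-52% |
| 29.7 months | 71% | 65-70% | 22.7-23.8 | about 52-56% |

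If the 18 months ran from entry of the 6th arm A patient, the share would be 61-69% without attrition. If they ran from the 30th patient, the 30-completer trigger would come first.

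**Step 4: who has been seen at month 18.** On the stated dates, 22-24 arm A patients have entered and 15-17 have finished 6 cycles. Another 24-27 have not yet been enrolled. Nobody can have finished 24 cycles, which take 672 days, about 22 months.

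**The case against.** The strongest reply has five parts.

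1. **The trigger is not the data.** Both passages say that all patients are reviewed, so early stoppers are seen once the committee meets. This stands. The defect is in when the review happens, not in what it covers.
2. **Stopping carfilzomib alone may not remove a patient from the count.** Section 11.3.2.1 keeps a patient on ibrutinib on treatment. This stands in part: the protocol does not say whether such a patient has completed 6 cycles of treatment for this purpose.
3. **The mandate is wider than two meetings.** A reader might infer that the DSMC stops after its second review. No passage says so: section 15 speaks of review throughout the study, and the charter may schedule more. What remains is that the protocol fixes the timing of two reviews itself and does not reconcile that with its general statement.
4. **Serious cardiac toxicity comes early.** Section 7.5 reports that it typically appears before cycle 5, which 6-cycle reviews capture. That holds within a patient. Yet on the stated dates about half of arm A is not enrolled at month 18, so those patients' early cycles also fall after the last scheduled review.
5. **Both reviews have probably passed.** The protocol version is dated 14.03.2024. Month 18 from first patient in was about August 2022, and the 30th completer would fall between about January and August 2023. Rewording the triggers may then change little, but the missing later reviews can still be added.

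Other safeguards exist: closer monitoring of the first 10 arm A patients, sponsor safety monitoring and regulatory safety reports. None of these is a committee review.

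**Conclusion.** The point holds as a badly fixed rule that is cheap to repair, and it should be changed. Both patient-count triggers rest on completers, the first review has no calendar limit of its own, its two wordings differ, and nothing is scheduled after the second review.

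The delay to the first review is moderate: about 1.5 to 2 months at 30% non-completion and 3.6 to 4.8 months at 50%. Both rates are assumed, and it is also assumed that stoppers do not count. If the 18-month limit runs from first patient in, it also bounds the wait indirectly, because the second review then takes place regardless.

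Two stronger readings are tempting and not supported:

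- **That the first review might never happen.** This takes section 15 to mean the first six patients enrolled, all of whom must complete. At assumed stopping rates of 10%, 20% and 30%, the chance of that is 0.9⁶ = 53%, 0.8⁶ = 26% and 0.7⁶ = 12%. The synopsis reads as the 6th completer, which one early stopper does not block.
- **That about 80% of exposure follows the last review.** That figure needs patient-time instead of dose, no attrition and a clock starting at first patient in. By dose, the range is roughly 65-78% with that clock, and about half if the 30-patient trigger governs.

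**What to change.** In section 15, the synopsis and the charter:

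1. Use one wording for the first trigger in both places.
2. For both reviews, count arm A patients who have completed 6 cycles or have permanently discontinued study treatment (either drug) before then. This also settles how a patient who stops only carfilzomib is counted.
3. Give the first review a latest calendar date.
4. State when the 18-month clock starts.
5. State periodic DSMC safety reviews, for example yearly, until the last arm A patient has finished carfilzomib. If the charter already provides them, say so in section 15.

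If the first two reviews have already taken place, item 5 is the one that still matters most. The cost is a wording change and a few more meetings of the existing committee. It needs no new patients, visits or data.
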